### **7.2 Handling of CPI-613**

CPI-613 is an investigational drug and its toxicity in humans is not fully understood. All necessary precautions in handling potentially toxic chemicals must be strictly adhered to. Gloves and protective clothing must be worn when handling CPI-613. Avoid contact by all modes of exposure. If the solution contacts the skin, it must be washed immediately and thoroughly with soap and water. If the solution comes in contact with mucous membranes, the membranes must be flushed thoroughly with water. Spills should be picked up with absorbent material and the area must be washed at least 3 times with ethyl alcohol followed by water.

CPI-613 drug product is slightly photosensitive (Study# PHO-001). Therefore, after removal of CPI-613 drug product from the amber vials, CPI-613 drug product should be protected from

excessive light before administration to patients.

### **7.3 Storage of CPI-613**

CPI-613 should be stored under refrigeration, at 2°-8°C (36°-46°F), except when being prepared for administration.

### **7.4 IV Infusion Sets, Syringes and IV Bags to be used for Administration of CPI-613**

CPI-613 must be administered IV by infusion, via an IV catheter with D5W running at a rate of about 125-150 mL/hr. To avoid local reactions at and around the site of administration, CPI-613 should be administered via a central venous catheter. Subsequent sections describe the appropriate types of IV catheters, IV bags, syringes and clinical solutions that can be used in mixing and administering CPI-613 to patients.

Leaching of Diethylhexyl Phthalate (DEHP): CPI-613 can cause leaching of DEHP from IV infusion sets and IV bags (Study COM-003). Therefore, DEHP-containing IV infusion sets, IV bags or syringes should not be used in mixing or administration of CPI-613. Examples of the IV sets, IV bags and syringes that do not contain DEHP and therefore can be used in the administration of CPI-613 are:

Extension Set for Syringe Pump Use: All extension sets from MED-RX do not contain DEHP.

Syringes: All Monoject syringes are DEHP free.

IV Infusion Sets: A compatibility study has been conducted showing that CPI-613 is compatible with 4 commonly used IV infusion sets (Study# COM-001). Therefore, these 4 types of IV infusion sets, and IV infusion sets that are made with the same materials, can be used to administer CPI-613. These IV infusion sets are:

- PVC material - ADDitIV® Primary IV Set with Universal Spike, Backcheck Valve, 2 Injection Sites, DEHP-Free and Latex-Free, 15 drops/mL, REF V14453, B Braun Medical Inc.
- Latex material - Interlink® System Secondary Medication Set, 10 drops/mL, 2C7451, Baxter Healthcare Corporation
- PVC material - Surshield™ Safety Winged Infusion Set, 0.19 mL Volume, Latex-Free, DEHP-Free, SV\*S25BLS, Terumo Medical Products Hangzhou Co. Ltd.
- Polyethylene material - Interlink® System Paclitaxel Set by Baxter HealthCare, Non DEHP-free: Polyethylene tubing with a 0.22 microfilter Item # 2C7558 10 drops/mL

Syringes: Compatibility studies (Studies# COM-001 and COM-002) have shown that CPI-613 drug product (50 mg/mL), and drug product diluted with D5W to various concentrations (1.6-25 mg/mL) are compatible with various types of syringes, as listed below. Therefore, any of these types of syringes, and syringes that are made with the same materials, can be used to administer CPI-613. Also, glass syringes can also be used, since glass (such as glass containers) is compatible with CPI-613 drug product.

- Norm-Ject, polyethylene barrel, polyethylene plunger, latex free (Henke Sass

- Wolf GMBH) syringes
- Becton Dickinson syringes
- Terumo syringes
- Monoject syringes
- Glass syringes

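### Section 7.4 bars DEHP-containing infusion sets, yet one of the four sets it permits carries a descriptor that, read literally, says it is not DEHP-free

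*Combined protocol and SAP*

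**What the plan says.** All the relevant text is in Section 7.4, which covers the equipment for giving CPI-613.

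- **Hazard.** Citing Study COM-003, the section says that the drug can cause DEHP to leach from infusion sets and bags.
- **Bar.** It concludes that "DEHP-containing IV infusion sets, IV bags or syringes should not be used in mixing or administration of CPI-613".
- **Lead-in.** It introduces its examples as items "that do not contain DEHP and therefore can be used in the administration of CPI-613".
- **Permission.** For infusion sets it relies on a compatibility study, COM-001, and says that "these 4 types of IV infusion sets, and IV infusion sets that are made with the same materials, can be used to administer CPI-613".
- **Fourth permitted set.** This entry, a paclitaxel set, carries the descriptor "Non DEHP-free: Polyethylene tubing with a 0.22 microfilter".

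**The concern.** The descriptor on the fourth set says the opposite of what the lead-in promises. A pharmacist or nurse who takes the list as the instruction would regard the set as approved. One who takes the bar as the instruction, and reads the descriptor as it stands, would regard the same set as forbidden. The section gives no rule for choosing between the two.

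This matters more than a misprint in background text because Section 7.4 tells staff which equipment to use. Section 7.5, which repeats the precautions for administration, does not mention DEHP, so nothing later in the drug-handling instructions would catch the conflict. The instruction also applies repeatedly. Section 6.0 and Table 6-1 give a two-hour infusion on Days 1 to 5 of every four-week cycle, and Section 6.3 sets no maximum number of cycles.

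**Working it through.** No arithmetic applies, and the plan gives no figure to reproduce. The check sets the statements in Section 7.4 beside one another.

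**Step 1: what each listed set says about DEHP.**

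| Listed set | Stated material | DEHP descriptor |
|---|---|---|
| First (primary IV set) | PVC | DEHP-free |
| Second (secondary medication set) | Latex | None given |
| Third (winged infusion set) | PVC | DEHP-free |
| Fourth (paclitaxel set) | Polyethylene | "Non DEHP-free: Polyethylene tubing with a 0.22 microfilter" |

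The count is two labelled free of DEHP, one with no label and one labelled in the opposite sense: 2 + 1 + 1 = 4.

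**Step 2: compare the labels with the bar.** The bar covers any set that contains DEHP. The first and third sets clear it on their own labels. The second neither clears nor fails it on its label. The fourth, read literally, fails it.

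**Step 3: compare the labels with the permission.** The permission covers all four sets without exception. The fourth set is therefore both permitted and, read literally, barred.

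**Step 4: does the conflict depend on the lead-in?** The lead-in presents the examples as free of DEHP, but the infusion sets also have their own introduction, based on compatibility. One could argue over which introduction governs the list. The conflict survives either way, because it needs only the bar, the permission and the descriptor.

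**Step 5: does another passage resolve it?** Section 7.5 gives dilution and administration precautions without mentioning DEHP. The reference list gives only the titles and dates of the cited studies: COM-001 on compatibility with infusion sets (2006) and COM-003 on DEHP release (2009). Nothing supplied qualifies or corrects the descriptor. The dates allow the possibility that the list of sets was drawn up before the DEHP rule and never aligned with it, but that is an inference.

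**Step 6: which reading is more likely?** Three features point to a slip for non-DEHP or DEHP-free:

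- The entry gives the material as polyethylene twice.
- The title of COM-003 in the reference list concerns DEHP release from sets and bags containing polyvinyl chloride.
- The lead-in says that the examples contain no DEHP.

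These make a slip plausible but do not prove it. The set's actual status rests on product labelling and study reports that were not supplied.

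**The case against.** The strongest reply is that this is a typing error with an obvious meaning. The material is polyethylene, the leaching report concerns a different plastic, and the sentence above the list says that the items contain no DEHP. The general bar is also stated before the list, so staff are warned before they reach the fourth entry. Much of this stands. A slip is a fair reading, and the point should be put as a query about wording. It does not remove the defect, because a slip here would reverse the meaning of a safety descriptor in a list that staff are told they may rely on.

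The objection also rules out four stronger readings that a reader might infer.

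- *That the fourth set contains DEHP, or that patients would be exposed to it.* The documents do not establish this. Exposure would require that the set does contain DEHP and that it was used despite the bar.
- *That DEHP exposure could be mistaken for CPI-613 toxicity.* The documents give no DEHP quantity, no DEHP toxicity profile and no overlap with the adverse events listed in Section 8.1. No such claim is made here.
- *That the latex set is a second contradiction.* Its entry, "Latex material - Interlink® System Secondary Medication Set, 10 drops/mL, 2C7451, Baxter Healthcare Corporation", simply carries no DEHP label. That is missing detail, and if the lead-in governs the list, its status is already stated.
- *That the wording allowing sets of the same materials extends the problem to DEHP-containing sets.* For the disputed entry the stated material is polyethylene. On the text, the extension reaches other polyethylene sets and says nothing about DEHP in them.

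**Conclusion.** The point holds as an internal inconsistency in an operative instruction. Section 7.4 bars DEHP-containing sets and permits four sets, one of which is described, read literally, as not free of DEHP. Its size is one entry out of four.

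The conclusion rests on the wording as supplied and on the absence of any correcting passage. It does not rest on any assumption about the set's composition: the text needs reconciling whether the descriptor is a slip or is accurate. The primary response rate, progression-free and overall survival, the planned confidence interval and the sample size of 20 are unaffected.

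**What to change.** The sponsor should confirm the DEHP status of the fourth set from its product labelling and from the COM-001 and COM-003 reports, both already cited. It should then amend Section 7.4 so that the descriptor, the permission and the prohibition agree and the instruction can be read in only one way. The answer depends on what those sources show, and this review does not say which set should be used.

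While the section is open, the sponsor could also state the DEHP status of each listed set in the same form. That would be an improvement in clarity, not the correction of an error.

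The cost is a check of the label and two existing reports, and about one line of protocol wording. The reconciliation itself requires no change to sample size or analysis.

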## 7.5 Reconstitution and Administration of CPI-613

CPI-613 must be diluted from 50 mg/mL to 12.5 mg/mL with 5% Dextrose Water or D5W (i.e., 1 portion of CPI-613 diluted with 3 portions of D5W) prior to administration. The diluted drug product should be visually inspected for clarity. If haziness, precipitate or coloration (other than colorless) is observed, do not use the diluted drug product for dosing. After dilution with sterile D5W, the solution is clear and has a pH of 8.4-8.8. The diluted CPI-613 drug product has been found to be stable for 24 hrs at room temperature and refrigeration temperature (Studies STA-010).

CPI-613 must be administered IV, via an IV catheter that is free flowing and free of air in the dead space of the IV catheter, to minimize vascular irritation, inflammation and acute toxicity of CPI-613 (Study NCL-049). Accidental co-administration of extra air in the dead space of IV catheters during administration of CPI-613 has demonstrated the potential to induce acute toxicity of CPI-613 according to animal studies (Study NCL-049). Also, accidental leakage of CPI-613 into the perivascular space during IV administration, which prolongs exposure of perivascular tissue to CPI-613, can induce significant local inflammation according to animal studies (Studies NCL-027 and NCL-030). To avoid local reactions at and around the site of administration, CPI-613 must be administered via a central venous catheter.

CPI-613 must not be administered as a bolus, but by infusion, at a rate of ~0.5 mL/min, via a central venous catheter with D5W running at a rate of about 125-150 mL/hr. This is to minimize potential acute toxicity of CPI-613, according to animal studies (Study NCL-049).

The following precautions must be taken when administering CPI-613:

- A. Confirmation of the placement of the IV line to ensure a lack of leakage of CPI-613 into the perivascular space.
- B. Confirmation that the IV line is free flowing.
- C. Confirmation that the IV line is free of dead air space.
- D. Dilute CPI-613 drug product with D5W, as instructed in the study protocol.
- E. Administer CPI-613 by infusion, not as a bolus.
- F. After administration of CPI-613, flush the IV line with ~10 mL of D5W to remove residual CPI-613.
- G. To avoid local reactions at and around the site of administration, CPI-613 should be administered via a central venous catheter.

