**Table 5-1: Study Procedures**

Assessments	Pre-study 	Each Treatment Cycle (1 cycle = 4 weeks)					Follow-Up
		Day 1	Day 2	Day 3	Day 4	Day 5	
Medical history	✓						
Physical exam, height, weight, vitals	✓	✓ 					
Pregnancy test	✓						
Evaluation of symptoms and vital signs	✓	✓ 	✓ 	✓ 	✓ 	✓ 	
ECOG performance status and survival	✓	✓ 					
Clinical chemistry, hematology and coagulation 	✓	✓ 					
BMP			✓	✓	✓	✓	
CPI-613 		✓	✓	✓	✓	✓	
Assessment of response 		Cycles 2, 4, 6 (and every 3 cycles thereafter until disease progression)					
Bone marrow exam 	✓	Cycles 3 and 6 (and at the discretion of the physician or if peripheral blood criteria for a complete remission are met (ie ANC>1000, Platelets>100k and freedom from blood transfusions) thereafter until disease progression)					
Survival and post-study follow-up 							✓

CR = Complete Remission; D1 = day 1; D4 = day 4; ECOG = Eastern Cooperative Oncology Group; hr = hour; min = minute; PR = Partial Remission.

 CPI-613 is given as a 2-hr IV infusion via a central venous catheter.

 These tests are performed with results available for review within 24 hrs before administration of the anti-tumor agents.

 Specific chemistry, hematology and coagulation are listed in section 5.2.2. Renal function will be assessed utilizing the Cockcroft-Gault formula.

 Cycles 2, 4, 6 (and every 3 cycles thereafter until disease progression).

 Survival and post-study cancer treatment will be monitored by the treating physician during routine follow-up visits for 5 years or until death.

 CR, marrow CR, and PR will be assessed using hematology results from blood work and bone marrow exam results, according to the criteria described by Cheson et al. (2006).

 Frequency of transfusion is defined as the number of transfusions received during the previous 8 weeks. The baseline assessment should reflect the number of transfusions received in the 8 weeks prior to enrollment. On-treatment assessments should be performed at the end of cycles 2, 4, and 6, and every 3 cycles thereafter until progression)

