**Table 6-1: Administration of CPI-613 in MDS Patients Who Has Failed Previous Agents**

Treatment Cycles		Administration of CPI-613	
	Week	Day	
Cycle 1 (4 weeks)	1	1	2-hr IV infusion via a central venous catheter
		2	2-hr IV infusion via a central venous catheter
		3	2-hr IV infusion via a central venous catheter
		4	2-hr IV infusion via a central venous catheter
		5	2-hr IV infusion via a central venous catheter
	2		
	3		
	4		
Cycle 2 (4 weeks)	1	1	2-hr IV infusion via a central venous catheter
		2	2-hr IV infusion via a central venous catheter
		3	2-hr IV infusion via a central venous catheter
		4	2-hr IV infusion via a central venous catheter
		5	2-hr IV infusion via a central venous catheter
	2		
	3		
	4		Bone marrow biopsy (week 4 of cycles 3 and

			6, then at the discretion of the physician or if peripheral blood criteria for a complete remission are met (ie ANC>1000, Platelets >100k and freedom from blood transfusions) thereafter until disease progression)
Etc., until termination of treatment as described in Section 6.3.			

hr = hour; IV = intravenous; min = minutes

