## 6.1 Sample Size, Dose Levels and Justification of the Dose

The sample size will be 20 for this pilot trial.

The dose will be the maximum tolerated dose (MTD) determined from CCCWFU 22112, entitled *“An Open Label, Dose-Escalation Study to Evaluate Safety, Tolerability, Maximum Tolerated Dose (MTD), Efficacy, and Pharmacokinetics (PKs) of CPI-613 given with High Dose Cytarabine and Mitoxantrone in Patients with Relapsed or Refractory Acute Myeloid Leukemia (AML)”*, sponsored by [name]. This dose was determined to be 2500mg/m^2.

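### The ~0.5 mL/min infusion rate in Section 7.5 cannot deliver 2500 mg/m² at 12.5 mg/mL in 2 hours; it needs 6.67 hours per m² of body surface

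*Combined protocol and SAP*

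**What the plan says.** Four instructions fix how each dose is given.

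- **Dose.** Section 6.1, on the maximum tolerated dose taken from the earlier leukaemia study: "This dose was determined to be 2500mg/m"². Section 7.9 scales the amount to the patient's body surface area (BSA).
- **Dilution.** Section 7.5: "CPI-613 must be diluted from 50 mg/mL to 12.5 mg/mL with 5% Dextrose Water or D5W".
- **Rate.** Section 7.5: "CPI-613 must not be administered as a bolus, but by infusion, at a rate of ~0.5 mL/min". The same paragraph gives the reason as limiting acute toxicity, citing animal Study NCL-049.
- **Duration.** Table 5-1, footnote 1: "CPI-613 is given as a 2-hr IV infusion via a central venous catheter". Table 6-1 repeats the 2-hour entry for Days 1 to 5 of each cycle shown.

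Two further statements bear on the question. Sections 7.4 and 7.5 have the drug go in "via an IV catheter with D5W running at a rate of about 125-150 mL/hr", which describes the carrier line. Section 1.2.1 reports that doses up to 3,000 mg/m² over 2 hours were well tolerated in Phase I.

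**The concern.** Dose and concentration determine the volume, and volume and rate determine the duration. Once the first three instructions are set, the fourth is no longer free, and the 2-hour entry does not follow from the other three. No text available for this review limits the rate to part of the infusion, scales it by body size, or otherwise links it to the 2-hour duration.

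Section 7.5 is where a pharmacist or nurse looks for administration instructions, and it gives the only drug flow rate in the text reviewed. Someone who programs the pump from it and someone who works from the schedule tables would set very different rates for the same patient, on five days of every cycle. The delivered dose is at stake if the rate and the 2-hour stop are both applied. If the tables are followed instead, staff depart from a precaution that the protocol says is there for safety.

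**Working it through.** **Inputs from the protocol**

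- Dose: 2500 mg/m² (Section 6.1)
- Vial concentration: 50 mg/mL (Section 7.1)
- Diluted concentration: 12.5 mg/mL, one part drug to three parts D5W (Section 7.5); check: 50/4 = 12.5
- Drug rate: ~0.5 mL/min (Section 7.5)
- Duration: 2 h = 120 min (Table 5-1 footnote 1, Table 6-1)

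**Attempt to reproduce the 2-hour duration**

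1. Diluted volume = 2500 × BSA / 12.5 = 200 × BSA mL.
2. Time at 0.5 mL/min = 200 × BSA / 0.5 = 400 × BSA min = 6.67 × BSA h.
3. Volume given in 2 h at 0.5 mL/min = 0.5 × 120 = 60 mL.
4. BSA at which that is a full dose = 60/200 = 0.30 m².

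The 2-hour figure is not reproduced for any adult. The per-m² result needs no outside assumption.

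**Size of the conflict**

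- Rate needed for 2 h = 200 × BSA / 120 = 1.67 × BSA mL/min.
- Drug delivered if stopped at 2 h = 60 × 12.5 = 750 mg.
- As a fraction of the dose = 750 / (2500 × BSA) = 0.30 / BSA.

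The documents give no BSA. I assume 1.5, 1.8 and 2.2 m², with 1.2 m² as a sensitivity case.

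| BSA (m²) | Dose (mg) | Volume (mL) | Time at 0.5 mL/min (h) | Rate for 2 h (mL/min) | Multiple of 0.5 | Dose delivered in 2 h at 0.5 mL/min |
|---|---|---|---|---|---|---|
| 1.2 | 3000 | 240 | 8.0 | 2.0 | 4.0 | 25% |
| 1.5 | 3750 | 300 | 10.0 | 2.5 | 5.0 | 20.0% |
| 1.8 | 4500 | 360 | 12.0 | 3.0 | 6.0 | 16.7% |
| 2.2 | 5500 | 440 | 14.7 | 3.7 | 7.3 | 13.6% |

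**Readings that might reconcile the figures**

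- *The tilde.* At 0.45 to 0.55 mL/min the time is 7.41 to 6.06 h per m².
- *Reduced doses (Section 6.2).* After a 50% reduction the volume is 100 mL/m², so 2 h fits only at 60/100 = 0.60 m². At 1.5, 1.8 and 2.2 m² the infusion still takes 5.0, 6.0 and 7.3 h.
- *Undiluted drug.* The volume is 2500/50 = 50 mL/m², so 2 h fits only at 60/50 = 1.2 m². At 1.5 to 2.2 m² it takes 2.5 to 3.7 h. This reading also contradicts the dilution requirement.
- *The 125-150 mL/hr figure.* This is the D5W line. Misread as the drug rate, it would deliver 250 to 300 mL in 2 h, a full dose only at 250/200 = 1.25 to 300/200 = 1.5 m², and it would still conflict with 0.5 mL/min.

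None of these resolves the conflict at the assumed adult sizes.

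**The case against.** The strongest reply accepts the arithmetic and disputes its importance. The 2-hour duration appears in both schedule tables and in the Phase I experience. The 0.5 mL/min figure appears once, is marked approximate, and sits in a sentence whose main purpose is to rule out a bolus. The list of precautions that follows repeats the ban on a bolus but gives no rate. The figure may be left over from another setting; if it was derived for undiluted product, the gap shrinks to about 1.25 to 1.8-fold. A runtime of 10 hours or more against a 2-hour order would be plain when the pump is set, and the likely result is a call to pharmacy or the sponsor. Stopping at 750 mg would leave 80 to 86% of a prepared dose unused, and Section 7.7 requires doses to be accounted for.

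Much of this stands. The weight of the text favours 2 hours, and the 750 mg outcome is possible rather than probable. The documents do not show how likely either error is, or that either rate is toxic. Study NCL-049 and the text on earlier safety data (Section 1.2.2) were not available for this review.

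Two points remain. The rate is worded as mandatory and justified as an acute-toxicity precaution, so staff should not have to set it aside on their own judgment. Nor can the longer duration be dismissed on stability grounds: "The diluted CPI-613 drug product has been found to be stable for 24 hrs at room temperature and refrigeration temperature", and every duration in the table is within that limit.

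**Conclusion.** The concern holds. Rate, dilution, dose and duration are mutually incompatible, and the 6.67 h per m² result follows exactly from the protocol's own figures. The 5 to 7.3-fold difference in rate, the 10.0 to 14.7 h duration and the 14 to 20% delivered dose rest on an assumed BSA of 1.5 to 2.2 m² and on reading 0.5 mL/min as the flow of diluted drug, the natural reading of Section 7.5. The conflict remains at 1.2 m² and after a 50% dose reduction.

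Which figure is wrong cannot be settled from the documents. Confidence is high that the inconsistency exists and lower about its practical consequence. It concerns drug administration and safety only: the sample size of 20, the confidence interval for response and the descriptive analyses do not change. It should still be corrected, because an operative dosing instruction cannot be carried out as written.

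**What to change.** First, have the sponsor confirm which figure governs, given the safety reason attached to the rate.

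**If 2 hours governs**, replace the 0.5 mL/min figure in Section 7.5 with: *at a rate that delivers the full diluted volume over 2 hours (about 1.67 × BSA mL/min at 2500 mg/m², lower in proportion for reduced doses)*. The cost is one confirmation and a one-sentence amendment.

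**If 0.5 mL/min governs**, correct the 2-hour entries in Tables 5-1 and 6-1 to the duration that follows, about 6.67 h per m² at full dose. This is not cheap. At 1.5 to 2.2 m², each cycle would need 5 × 10.0 = 50 to 5 × 14.67 = 73 infusion hours instead of 10. Carrier D5W per dose would be 10.0 h × 0.125 L/h = 1.25 L to 14.67 h × 0.150 L/h = 2.2 L, instead of 0.25 to 0.30 L. Treatment days would have to be planned accordingly.
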